Official Title: Management of Spontaneous Ruptured Hepatocellular Carcinoma

- Partial Hepatectomy and Prognosis: A Retrospective Study

NCT number: Not available

Date of the document: 05/03/2018

Statistical analysis plan

All of the analyses were carried out using SPSS 24.0 (IBM), and a two-sided $P < 0.05$ was considered statistically significant.

1. A comparison of the clinicopathologic characteristics of all the patients between the partial hepatectomy group and the non-surgical treatment group before propensity score matching (PSM): there are (or no) significances for patients' characteristics before PSM.

The variables are: age, sex, HBs-Ag (+), HCV-Ab, tumor size, tumor number, macroscopic vascular invasion (MVI), cirrhosis, portal hypertension, Child-Pugh grade, hemorrhagic shock, hemoglobin, red blood cell (RBC), transfusion during hospitalization, a-fetoprotein (AFP), aspartate aminotransferase (AST), albumin, total bilirubin, Barcelona Clinic Liver Cancer (BCLC) stage, sorafenib, 30-day mortality.

Statistical analysis method: Pearson's χ^2 test, χ^2 test with Yates' correction, Fisher's exact test, Wilcoxon's rank-sum test and Student's t test.

2. Univariate and multivariate analysis of the predictive factors associated with overall survival (OS) before PSM: surgery or non-surgical treatment is (or not) an independent risk factor of overall survival.

The variables included are: age, sex, tumor size, tumor number, MVI, cirrhosis, portal hypertension, treatment, hemorrhagic shock, distant metastasis, AST, AFP, platelet, hemoglobin, sorafenib, Child-Pugh grade.

Statistical analysis method: univariate analysis was performed using the Kaplan-Meier method compared by the log-rank test; multivariate analysis was performed using the COX regression model.

3. A comparison of the clinicopathologic characteristics of all of the patients between the partial hepatectomy group and the non-surgical treatment group after PSM: there is no significance for patients' characteristics after PSM.

The variables included in PSM are: age, sex, tumor size, tumor number, MVI, cirrhosis, portal hypertension, hemorrhagic shock, hemoglobin, red blood cell (RBC), transfusion during hospitalization, a-fetoprotein (AFP), aspartate aminotransferase (AST), albumin, total bilirubin.

Statistical analysis method: PSM, a caliper of 0.5, 0.3, 0.2, 0.1, 0.05, 0.02, 0.01 would be used.

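### HBs-Ag, HCV-Ab and BCLC stage are compared between groups but are in neither the matching list nor the Cox lists, so residual confounding of the surgery effect is not excluded

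*SAP*

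**What the plan says.** Item 1 of the SAP sets out the pre-matching comparison of the partial hepatectomy and non-surgical groups. Its list opens with "age, sex, HBs-Ag (+), HCV-Ab, tumor size, tumor number" and closes with "Barcelona Clinic Liver Cancer (BCLC) stage, sorafenib, 30-day mortality". Viral status and BCLC stage are therefore collected and tabulated by treatment group.

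Item 3 gives the propensity score variables: "The variables included in PSM are: age, sex, tumor size, tumor number, MVI, cirrhosis, portal hypertension, hemorrhagic shock, hemoglobin", then red blood cell, and finally "transfusion during hospitalization, a-fetoprotein (AFP), aspartate aminotransferase (AST), albumin, total bilirubin". It also states the result in advance: "there is no significance for patients' characteristics after PSM".

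Item 2 lists the terms for the survival analysis before matching. Its second half reads "portal hypertension, treatment, hemorrhagic shock, distant metastasis, AST, AFP, platelet, hemoglobin, sorafenib, Child-Pugh grade". Item 4 repeats the same terms after matching. Both items use Kaplan-Meier with the log-rank test for the univariate analysis and a Cox model for the multivariate one.

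The SAP gives no reason for leaving HBs-Ag, HCV-Ab and BCLC stage out of items 2 to 4. It has no rule for carrying an imbalance seen in item 1 into the matching or the Cox models.

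**The concern.** Items 2 and 4 decide whether surgery is an independent factor for overall survival. In a retrospective, non-randomised comparison that answer depends on the covariate lists. Three characteristics that the plan itself compares between groups are never adjusted for directly.

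The exposure differs by variable:

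- **Viral status.** No listed covariate measures it. Cirrhosis, portal hypertension and AST are in the matching list and both Cox lists, but they are only partial proxies.
- **BCLC stage.** The Cox models hold tumour size, tumour number, MVI, distant metastasis and Child-Pugh grade. The matching list holds size, number and MVI, with albumin and bilirubin for liver function, but not distant metastasis or Child-Pugh grade. The matched Kaplan-Meier/log-rank comparison in item 4 has no covariate adjustment, so it relies on the matching alone. This is where a gap in stage matters.

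**Working it through.** **Step 1: compare the lists.** Counting terms as printed, with red blood cell and transfusion as two, item 1 has 21 variables, the matching list 15, and each Cox list 16 including treatment. The Cox lists of items 2 and 4 are identical. If red blood cell and transfusion are one variable, items 1 and 3 have 20 and 14, and nothing below changes.

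| Item 1 variable | Matching (item 3) | Cox (items 2 and 4) |
|---|---|---|
| HBs-Ag | no | no |
| HCV-Ab | no | no |
| BCLC stage | no | no |
| 30-day mortality | no | no |
| Child-Pugh grade | no | yes |
| Sorafenib | no | yes |
| Red blood cell, transfusion, albumin, bilirubin | yes | no |
| All other item 1 variables | yes | yes |

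Four item 1 variables appear in none of the later lists. One of them, 30-day mortality, is an outcome and is rightly left out. The other three are the subject of this point.

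**Step 2: what an omitted factor could do.** The SAP gives no prevalences, hazard ratios, sample size or event count, so every input here is an assumption. For an omitted binary factor with hazard ratio HRu for death, and prevalence p1 in the surgical and p0 in the non-surgical group, the surgery hazard ratio is multiplied by approximately

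(1 + (HRu − 1)·p1) / (1 + (HRu − 1)·p0).

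| Assumed case | HRu | p1 v p0 | Factor |
|---|---|---|---|
| No independent effect | 1.0 | any | 1.00 |
| Balanced | any | equal | 1.00 |
| HBs-Ag | 1.2 | 75% v 90% | 1.15/1.18 = 0.975 |
| HBs-Ag | 1.5 | 75% v 90% | 1.375/1.45 = 0.948 |
| Generic factor | 1.5 | 80% v 70% | 1.40/1.35 = 1.037 |
| Generic factor | 2.0 | 80% v 70% | 1.80/1.70 = 1.059 |
| Advanced BCLC, effect beyond the matched variables | 1.5 | 30% v 50% | 1.15/1.25 = 0.92 |
| Advanced BCLC, effect beyond the matched variables | 2.0 | 30% v 50% | 1.30/1.50 = 0.867 |

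The direction depends on which group has the higher prevalence. The BCLC rows further assume that the whole 30% v 50% imbalance survives matching on the components. They are an upper illustration, not an expectation.

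**Step 3: how much the listed covariates absorb.** A linear simulation with a true treatment effect of zero let the adjusted covariate explain a share R² of the omitted variable.

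| R² | Share of bias remaining |
|---|---|
| 0% | 100% |
| 50% | 53% |
| 80% | 21% |
| 95% | 5% |
| 100% | 0% |

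What remains is the part that predicts survival and is not explained by the listed covariates. For BCLC stage R² may be high, since several components are listed. The SAP does not define the stage, so the overlap cannot be computed. For viral status R² with cirrhosis, portal hypertension and AST is unknown.

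**The case against.** The strongest reply is that a plan need not adjust for every baseline descriptor, and that these three are largely covered. BCLC stage is a summary of features that mostly appear elsewhere in the lists. The Cox models, including the one after matching, hold its tumour components and Child-Pugh grade. Nothing in the SAP shows that viral markers predict overall survival once cirrhosis, portal hypertension and AST are adjusted for. Without a sample size or event count, the cost of extra terms cannot be checked either.

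Much of this stands. It removes the case for adding BCLC stage to the Cox models and leaves the size of any confounding unknown. It does not cover viral status, which has no direct term in any adjustment, or the matched log-rank comparison, which cannot draw on the Cox covariates.

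Two stronger readings are tempting, and the SAP supports neither:

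- A reader might infer that any difference found in item 1 passes whole into the surgery effect. Step 3 shows that it does not when the variable is related to listed covariates.
- A reader might infer that item 3's statement of no significant differences after matching is wrong for these three variables. Item 3 gives no comparison list apart from the matching variables, so it is not established that the statement covers them. Balance could also arise through correlated covariates.

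**Conclusion.** The point holds in limited form. HBs-Ag, HCV-Ab and BCLC stage are compared between groups but used in no adjustment, with no reason given and no rule for acting on an imbalance. Residual confounding is therefore not excluded: by viral status in items 2 and 4, and by the uncaptured part of BCLC stage in the matched log-rank comparison.

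The SAP fixes neither size nor direction. On the assumed inputs, HBs-Ag moves the surgery hazard ratio by about 3-5%. Advanced BCLC stage moves it by 8-13%, but only if a sizeable effect and imbalance both survive matching on its components. The shift is nil if the groups are balanced on these variables or the variables have no independent effect on survival. This is an inexpensive improvement to the plan, not evidence that its result would be wrong.

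**What to change.** - Item 3: add HBs-Ag, HCV-Ab and BCLC stage to the propensity score variables (15 terms become 18).
- Items 2 and 4: add HBs-Ag and HCV-Ab to the Cox lists (16 terms become 18). Leave BCLC stage out of these models, which already hold its components.
- Item 3: report post-match balance for all three variables by name.

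If any of the three is left out on purpose, one sentence giving the reason would serve instead.

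The variables are already collected for item 1, so only the SAP wording changes. The cost is two more Cox terms and possibly slightly fewer matched pairs, most likely at the tightest of the listed calipers (down to 0.01). The number of pairs lost cannot be estimated, because the SAP gives no sample size.

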4. Univariate and multivariate analysis of the predictive factors associated with OS after PSM: surgery or non-surgical treatment is (or not) an independent risk factor of overall survival.

The variables included are: age, sex, tumor size, tumor number, MVI, cirrhosis, portal hypertension, treatment, hemorrhagic shock, distant metastasis, AST, AFP, platelet, hemoglobin, Sorafenib, Child-Pugh grade.

Statistical analysis method: univariate analysis was performed using the Kaplan-Meier method compared by the log-rank test; multivariate analysis was performed using the

COX regression model.

5. Comparison of OS and recurrence-free survival (RFS) between the emergency partial hepatectomy group and the staged partial hepatectomy group.

Statistical analysis method: univariate analysis was performed using the Kaplan-Meier method compared by the log-rank test.

6. Comparison of OS and RFS between the staged early partial hepatectomy group and the staged late partial hepatectomy group.

Statistical analysis method: univariate analysis was performed using the Kaplan-Meier method compared by the log-rank test.

7. Difference in 30-day mortality of peritoneal dissemination between the groups at different times.

Statistical analysis method: Pearson's χ^2 test, χ^2 test with Yates' correction and Fisher's exact test.

8. Univariate and multivariate logistic regression analysis of postoperative peritoneal dissemination.

The variables included are: age, sex, tumor size, tumor number, MVI, cirrhosis, estimated intraperitoneal bleeding, Child-Pugh grade, tumor differentiation, resection margin, type of hepatectomy, timing of hepatectomy.

Statistical analysis method: univariate and multivariate logistic regression analysis.

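### Child-Pugh grade, distant metastasis and platelet are left out of the propensity score although item 4 treats them as survival factors, so the matched log-rank comparison can still favour surgery

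*SAP*

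**What the plan says.** Item 1 compares "all the patients between the partial hepatectomy group and the non-surgical treatment group before propensity score matching (PSM" and has the grade among the baseline characteristics: "portal hypertension, Child-Pugh grade, hemorrhagic shock, hemoglobin, red blood cell (RBC". Items 2 and 4 include it again in the OS analyses before and after matching. The item 4 list ends "AST, AFP, platelet, hemoglobin, Sorafenib, Child-Pugh grade" and also contains distant metastasis.

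Item 3 is headed "A comparison of the clinicopathologic characteristics of all of the patients between the partial hepatectomy group and the non-surgical treatment group after PSM". Its matching variables start with "age, sex, tumor size, tumor number, MVI, cirrhosis, portal hypertension, hemorrhagic shock, hemoglobin, red blood cell (RBC", continue with in-hospital transfusion, and end with "a-fetoprotein (AFP), aspartate aminotransferase (AST), albumin, total bilirubin". As punctuated that is 15 variables, and the list is closed.

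Item 4 then plans two OS analyses on the matched patients: Kaplan-Meier curves with a log-rank test, which are unadjusted, and a Cox model with the listed variables. The test level is set once for the whole plan: "a two-sided $P < 0.05$ was considered statistically significant".

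**The concern.** Matching is meant to make the two groups alike in whatever drives both the choice of surgery and survival. Child-Pugh grade summarises liver reserve, so it plausibly does both. The SAP itself regards it as relevant to survival and has it recorded, yet omits it from this step. The same holds for distant metastasis and platelet.

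If the non-surgical side of the matched set keeps more patients with poor liver reserve or metastatic disease, it gains deaths unrelated to having had no operation. The matched survival curves and log-rank test would then lean towards surgery. Readers give those curves special weight because they come from a matched set.

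**Working it through.** **Plan's own figure.** The SAP states no sample size, event count or effect size, so there is nothing to reproduce. The check compares the lists and then illustrates the size.

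**Step 1: item 4 variables against item 3.**

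| Item 4 variable (other than treatment) | In the item 3 match? |
|---|---|
| age, sex, tumour size, tumour number, MVI, cirrhosis, portal hypertension, haemorrhagic shock, AST, AFP, haemoglobin | yes (11) |
| Child-Pugh grade, distant metastasis, platelet | no (3) |
| sorafenib | no (1) |

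Sorafenib is a treatment, and the SAP does not say when it was given relative to the surgical decision, so its absence from the score is not counted here. Distant metastasis and platelet are also missing from the item 1 list, so no listed table would show an imbalance in them.

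**Step 2: what the matched liver variables cover.** By its usual definition Child-Pugh grade combines albumin, bilirubin, ascites, encephalopathy and coagulation. Item 3 matches the first two, plus cirrhosis and portal hypertension as related markers. Two patients equal on all four can still have different grades.

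**Step 3: size in an unmatched, unadjusted comparison.** All inputs are assumptions: equal groups, true surgery HR 1, exponential OS with median 8 months (λ = ln 2 / 8 = 0.0866 per month), and a share p of the non-surgical group only being non-resectable with k times the hazard.

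- Surgery: S1(t) = exp(−λt).
- Non-surgical: S0(t) = (1−p)·exp(−λt) + p·exp(−kλt).
- With f1 and f0 the matching densities, the Cox estimate β solves ∫ [f1 − (f1+f0)·e^β·S1 / (e^β·S1 + S0)] dt = 0 over follow-up.

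| Follow-up | k | p = 10% | p = 20% | p = 30% |
|---|---|---|---|---|
| uncensored | 2 | 0.95 | 0.90 | 0.85 |
| uncensored | 3 | 0.93 | 0.87 | 0.81 |
| 24 months | 2 | 0.95 | 0.89 | 0.84 |
| 24 months | 3 | 0.93 | 0.86 | 0.79 |

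At 12 months and p = 30% the values are 0.82 (k = 2) and 0.75 (k = 3). Shorter follow-up gives lower values because the gap is widest at the start. For p = 30% and k = 3 the HR at time zero is 1/(0.7 + 0.3×3) = 0.63, and it drifts towards 1 as the high-risk patients die.

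**Step 4: does partial matching remove it?** A null simulation (true HR 1) used 400 patients and five liver components with correlation 0.3 or 0.6. Grade C was never resected and grade B less often. Mortality HRs for B/C against A were 1.5/2.5 or 2/4. Matching was 1:1 on tumour burden and two liver components, with a caliper of 0.2 or 0.02 and 50 to 120 runs per setting. Cirrhosis and portal hypertension were not modelled separately.

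| | Grade not in score | Grade in score (2/4, caliper 0.2) |
|---|---|---|
| grade C among non-surgical, before matching | 19–26% | 19–26% |
| grade C among matched controls | 12–13% | 0% |
| unadjusted HR | 0.82–0.89 | 0.93 |
| false-positive rate (nominal 5%) | 12–32% | about 2% |
| Cox HR adjusted for grade and tumour burden | 0.97–1.01 | 0.98–0.99 |

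Tightening the caliper to 0.02 did not remove the grade C controls. The unadjusted HR of 0.93 with grade in the score shows that not all of the bias at that wide caliper came from the missing grade.

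**The case against.** The strongest reply is that the SAP judges whether treatment is an independent factor from the Cox models of items 2 and 4, and both list Child-Pugh grade. This largely stands: in Step 4 the adjusted HR returned to 0.97–1.01, given a correctly specified model. The SAP does not say how the grade is coded or whether every listed variable stays in the multivariate model, so the protection is likely but not assured. It does not extend to the matched curves or the log-rank test.

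It is also fair that liver function is not ignored in the match: albumin, bilirubin, cirrhosis and portal hypertension are all there. They shrink the problem but do not close it.

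A reader might infer from the references to all patients that the comparator contains people who could never have been resected. The SAP does not establish that. Cohort eligibility commonly sits in the protocol, which is not shown, and the wording may mean all eligible patients.

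A reader might also infer that the item 2 Cox model, lacking overlap in the worst grade, would itself make surgery look protective. That does not follow. If the grade enters as categories, a grade without resected patients gets its own coefficient, and the treatment effect is estimated essentially from grades containing both treatments. This limits the population described; it does not by itself create a benefit.

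**Conclusion.** The point holds for the matched comparison. Three variables that the SAP counts as OS factors after matching are absent from the score, and the matched Kaplan-Meier/log-rank analysis can stay confounded in favour of surgery. The Cox model in item 4 should remove much of the part due to Child-Pugh grade, without giving a direct comparison in any grade that has no resected patients.

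The size cannot be determined from the SAP, which gives no shares or hazards. The uncensored HRs of 0.95 to 0.81 describe an unmatched, unadjusted comparison under assumed inputs. They are neither an estimate for this cohort nor a strict bound: short follow-up lowers them and partial matching on liver function moves them towards 1. Neither calculation models distant metastasis or platelet; for those two the finding rests on the comparison of the lists alone.

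**What to change.** 1. Add Child-Pugh grade (as an exact match or a propensity-score variable), distant metastasis and platelet to the item 3 list.
2. Tabulate treatment by Child-Pugh grade and limit the matched OS comparison to grades with adequate numbers in both groups. State the minimum number before OS is examined, so that a single resected patient does not keep a whole grade in. Say that the conclusion applies to that population.
3. Report standardized differences for these three variables before and after matching.
4. Keep the all-patient analysis as a sensitivity analysis.

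The SAP already uses all three variables in item 4, so the cost is revised wording and a rerun of the match. The downside is fewer matched pairs and a narrower population for the conclusion.

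### Seven matching calipers are listed with no unit, no primary value and no selection rule, yet one OS conclusion is drawn after matching without naming the match

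*SAP*

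**What the plan says.** The title describes the study as "Partial Hepatectomy and Prognosis: A Retrospective Study". The opening paragraph sets one criterion for all analyses: "a two-sided $P < 0.05$ was considered statistically significant".

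Item 3 compares the two treatment groups after propensity score matching (PSM). Its list of PSM variables begins "The variables included in PSM are: age, sex, tumor size, tumor number, MVI, cirrhosis, portal hypertension" and has 15 entries if red blood cell and transfusion are counted separately, as printed. The method is one line: "PSM, a caliper of 0.5, 0.3, 0.2, 0.1, 0.05, 0.02, 0.01 would be used". On balance, item 3 says "there is no significance for patients' characteristics after PSM".

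Item 4 then analyses the factors "associated with OS after PSM: surgery or non-surgical treatment is (or not) an independent risk factor of overall survival", using Kaplan-Meier curves with the log-rank test, followed by a Cox model. The model has 16 terms: treatment and 15 covariates. The list ends "treatment, hemorrhagic shock, distant metastasis, AST, AFP, platelet, hemoglobin, Sorafenib, Child-Pugh grade". Item 4 mentions no caliper and no particular matched set.

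**The concern.** Each caliper can produce a different matched cohort, and the listed values span a 50-fold range (0.5 / 0.01). The SAP says that all seven will be used, then asks one question of the matched data and expects one answer. If the answers differ, nothing says which stands. The adjusted analysis of the unmatched cohort in item 2 cannot decide between matched results.

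The unit is also open. A caliper of 0.5 on the probability scale is very loose; 0.5 SD of the logit is much tighter. The unit can therefore decide whether the match removes confounding.

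The text does not say that a match will be picked by its outcome. But the study is retrospective, so OS can be known before a match is chosen, and the plan has no safeguard against that.

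**Working it through.** The SAP gives no sample size, event count or effect size, so it has no figure to reproduce. From the SAP come the seven calipers, the two-sided 0.05 level, the 15 PSM covariates and the 16-term model. Everything else below is assumed.

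**1. What non-significance allows.** For a continuous covariate and *m* matched pairs, the largest standardized mean difference (SMD) that a two-sample t test leaves non-significant is t(0.975, 2m−2) × √(2/m).

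| Pairs *m* | Largest non-significant SMD |
|---|---|
| 100 | 0.279 |
| 50 | 0.397 |
| 30 | 0.517 |

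For a given imbalance, the statement is easier to meet with fewer pairs.

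**2. Main simulation.**
- 1,000 datasets per cell; 300 or 150 patients; true HR 1, 0.7 or 0.5.
- The 15 PSM covariates plus the four that appear only in item 4.
- Six confounders (tumor size, tumor number, MVI, hemoglobin, albumin, bilirubin), with log-odds 0.35 per SD for treatment and log-hazard 0.25 per SD for death.
- 48% treated, 64–72% events, exponential event and censoring times.
- Greedy 1:1 matching without replacement. Balance is met if P ≥ 0.05 on all 15 covariates.

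With calipers in SD of the logit and 300 patients:

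| Caliper | 0.5 | 0.3 | 0.2 | 0.1 | 0.05 | 0.02 | 0.01 |
|---|---|---|---|---|---|---|---|
| Mean pairs | 101 | 97 | 95 | 92 | 87 | 72 | 55 |
| Balance met (%) | 100 | 99.8 | 100 | 99.9 | 99.6 | 96.7 | 88.8 |

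The pass rates sum to 684.8%, so about 6.8 to 6.9 of 7 calipers pass on average (6.9 in the run; 6.6 with 150 patients). All seven pass in 86% of runs with 300 patients and 70% with 150. The statement seldom narrows the list.

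**3. Do the seven answers agree?** Disagreement means at least one p < 0.05 and at least one not.

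| Runs with disagreement (%) | HR 1 | HR 0.7 | HR 0.5 |
|---|---|---|---|
| Log-rank, 300 patients | 9.3 | 42.8 | 25.6 |
| – balanced matches only | 9.3 | 41.4 | 24.0 |
| – four widest calipers only | 5 | 21 | 6 |
| 16-term Cox, 300 patients | 17.8 | 43.4 | 26.5 |
| Log-rank, 150 patients | 11.6 | 33.8 | 58.2 |
| – balanced matches only | 10.2 | 31.5 | 54.5 |

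The Cox model with 150 patients is left out, because at caliper 0.01 it could not be fitted in 72% of runs (fewer than 20 pairs). A rerun under similar inputs gave log-rank disagreement of about 10, 37 and 30% (300 patients) and 12, 29 and 55% (150).

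**4. Worst case: one result picked by outcome.** Seven tests at 0.05 give a chance of at least one false positive between 0.05 (fully dependent) and 1 − 0.95⁷ = 0.302 (independent); the Bonferroni bound is 7 × 0.05 = 0.35. The matched sets overlap, so the truth lies inside that range. In the main simulation the log-rank figure is 9.9% with 300 patients, against 2.7–4.8% for a single caliper, and 11.8% with 150 (single 3.3–4.3%). For the 16-term Cox model with 300 patients it is 18.8% (single 6.2–7.9%). A simpler simulation with one covariate and 1,500 replicates gave 8.8–16.3% on the logit-SD scale.

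**5. The unit.** In the one-covariate simulation with 150 patients, mean pairs fell from 67 to 38 on the probability scale and from 50 to 19 in SD of the logit. With a prognostic covariate, probability caliper 0.5 alone rejected a true null in 43.0% (150 patients) and 70.2% (300) of runs. In the main simulation (300 patients, true HR 1), probability caliper 0.3 met the balance statement in 95% of runs yet gave an unadjusted HR of 0.87 (0.95 in the 16-term model). Probability caliper 0.5 gave 0.78 but met the statement in only 16%.

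**The case against.** The best defence is that the calipers run in descending order beside a balance target, so the intent may be to tighten until no difference is significant and analyse that one match. Item 4 would then have one answer. In the main simulation, taking the widest balanced match gives a null log-rank rate of 4.6% (300 patients) or 3.5% (150) in SD of the logit, so no inflation. But the SAP does not state that rule; its sentence reads as an expected result. The defence also depends on the missing unit: on the probability scale the same rule gives 14.5% and 12.4%.

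Several limits do stand:
- Every simulated figure rests on assumed inputs. Across the one-covariate scenarios the any-of-seven null rate ran from 0.088 to 0.727, so none is an estimate for this study.
- Disagreement here means p values on different sides of 0.05, and part of it is lost power as pairs fall from 101 to 55.
- An independent-factor claim rests on the Cox model, while most figures are for the log-rank test. The Cox model's single-caliper null rate is already 6.2–7.9%, so its 18% is not purely a caliper effect.
- If the balance statement also covers the extra characteristics in item 1 (such as HBs-Ag or BCLC stage), it is stricter than simulated. On the probability scale it would exclude caliper 0.5 in most runs.
- Although non-significance is easier with fewer pairs for a fixed imbalance, overall pass rates in the simulation fell at tight calipers (to 88.8% with 300 patients and 75% with 150).

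These points bear on size. None supplies a unit, a primary caliper or the match that item 4 uses.

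**Conclusion.** The concern holds and should be corrected. The defect is visible in the text and needs no simulation: seven calipers without a unit feed one conclusion, and no match is designated. This is not a detail that could be left to a protocol, because the SAP itself specifies the caliper as a seven-value list.

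The size is indicative only. Under the assumed inputs and logit-SD units, nearly all calipers satisfy the balance statement, and the matched log-rank verdicts conflict in roughly 9% to 58% of runs, depending on true effect and sample size. With 300 patients and only the four widest calipers the range is 5% to 21%. The false-positive figures of about 10–12% for the log-rank test apply only if a result were chosen by outcome, which the SAP does not say.

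**What to change.** In item 3, name one primary match with its unit and algorithm, for example 1:1 nearest-neighbour matching with a caliper of 0.2 SD of the logit of the propensity score. Fix it without reference to OS results after matching, and state in item 4 that its conclusion is drawn on that match. Report the other six calipers side by side, with matched N, HR and confidence interval, as sensitivity analyses only.

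Report SMDs for all PSM covariates in place of P values as the balance measure, flagging values above 0.1. The flag must be descriptive: with 15 covariates at caliper 0.2 SD, at least one SMD exceeded 0.1 in 87% of simulated runs with 300 patients and 99% with 150, so it cannot serve as an acceptance rule.

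Item 4's 16-term model can stay as it is. If adjustment is wanted for the PSM covariates it omits (RBC, transfusion, albumin, total bilirubin), pre-specify that as a sensitivity analysis.

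The cost is SAP wording and one table of seven results, with no new data. The price is that the caliper can no longer be chosen after results are seen, and some covariates will be shown as imperfectly balanced.

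### OS and RFS by timing of hepatectomy (SAP items 5 and 6) rest on an unadjusted log-rank test alone, so differences in patient condition can be read as an effect of timing

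*SAP*

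**What the plan says.** Item 5 is a "Comparison of OS and recurrence-free survival (RFS) between the emergency partial hepatectomy group and the staged partial hepatectomy group". Item 6 is a "Comparison of OS and RFS between the staged early partial hepatectomy group and the staged late partial hepatectomy group". Under each stands the same single method line: "Statistical analysis method: univariate analysis was performed using the Kaplan-Meier method compared by the log-rank test". Neither item has a covariate list, a regression model, stratification or matching. The opening paragraph of the SAP applies a two-sided 5% significance level to all analyses, so these four tests (two comparisons, two endpoints) are covered by it.

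The other items treat confounding as follows:

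- **Items 1 and 3** compare baseline characteristics before and after propensity score matching. Both concern surgery against no surgery; item 3, for example, covers "clinicopathologic characteristics of all of the patients between the partial hepatectomy group and the non-surgical treatment group after PSM".
- **Items 2 and 4** add a multivariable Cox model for OS. The list includes "portal hypertension, treatment, hemorrhagic shock, distant metastasis, AST, AFP, platelet, hemoglobin, sorafenib, Child-Pugh grade". Its group variable is treatment (surgery or not); timing of surgery is not in it.
- **Item 7** is an unadjusted comparison of proportions between timing groups, not of OS or RFS.
- **Item 8** is the only adjusted model that contains timing ("resection margin, type of hepatectomy, timing of hepatectomy"). Its outcome is postoperative peritoneal dissemination.

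**The concern.** The title calls the study retrospective, so patients were not randomised to emergency, staged early or staged late surgery. If the groups differ in prognosis at presentation, an unadjusted log-rank test mixes that difference with any effect of timing.

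The plan accepts this reasoning elsewhere. For surgery against no surgery it does not stop at the log-rank test: it adds Cox adjustment for hemorrhagic shock, Child-Pugh grade, tumor size and other factors, and matching as well. For timing and peritoneal dissemination it also adjusts. Only for OS and RFS by timing does it stop at the univariate step, and RFS has no adjusted analysis anywhere in the document.

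At stake is how items 5 and 6 are read. A P value below 0.05 could be reported as a benefit or harm of a given timing when it reflects who was operated on when.

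**Working it through.** **Step 1: does any item supply the missing adjustment?**

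| Item | Contrast | Outcome | Adjusted? |
|---|---|---|---|
| 1, 3 | surgery v none | baseline characteristics | matching in item 3 |
| 2, 4 | surgery v none | OS | Cox, timing not listed |
| 5 | emergency v staged | OS, RFS | no |
| 6 | staged early v staged late | OS, RFS | no |
| 7 | timing groups | not OS or RFS | no |
| 8 | timing among covariates | peritoneal dissemination | logistic |

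No row gives an adjusted OS or RFS result by timing.

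**Step 2: how large could the distortion be?** The SAP states no sample size, event count or effect size, so there is no figure of its own to reproduce. What follows is an illustration. Only the two-sided 5% level (critical value 1.96) comes from the document.

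Assumed: true timing HR 1.0; one binary prognostic factor (shock); exponential survival with median 18 months (OS) or 10 months (RFS) without shock; uniform censoring at 12-60 months; equal groups.

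*Apparent HR.* Let group g have shock proportion p_g, and let the hazards be λ₀ = ln 2 / median and λ₁ = λ₀ × HR_shock. With G(t) the probability of being uncensored:

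- at risk: r_g(t) = G(t)[p_g e^(−λ₁t) + (1 − p_g) e^(−λ₀t)]
- event rate: f_g(t) = G(t)[p_g λ₁ e^(−λ₁t) + (1 − p_g) λ₀ e^(−λ₀t)]

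The large-sample unadjusted log HR is the b that solves ∫ { f₁ − (f₁ + f₀) · r₁e^b / (r₁e^b + r₀) } dt = 0.

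| Item | Shock, group 1 v 2 | Shock HR | OS HR (reversed) | RFS HR (reversed) |
|---|---|---|---|---|
| 5 | 40% v 20% | 1.5 | 1.08 (0.92) | 1.08 (0.93) |
| 5 | 40% v 10% | 2.0 | 1.21 (0.83) | 1.19 (0.84) |
| 6 | 30% v 20% | 1.5 | 1.04 (0.96) | 1.04 (0.96) |
| 6 | 30% v 10% | 2.0 | 1.14 (0.88) | 1.12 (0.89) |

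*False-positive rate.* With d events and equal groups, δ = |b|√d / 2 and the rejection rate is Φ(−1.96 + δ) + Φ(−1.96 − δ). For item 5, OS:

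- 50 per group, milder case: b = ln 1.082 = 0.079, d ≈ 75, δ = 0.34, rejection 6.3% (simulation 6.6%).
- 50 per group, stronger case: b = ln 1.212 = 0.192, d ≈ 76, δ = 0.84, rejection 13.3% (simulation 13.5%).
- 100 per group: δ = 0.48 and 1.18, rejection 7.7% and 21.9% (simulation 7.9% and 22.1%).

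For item 6, with 30 or 50 per group, simulated rejection is 5.3-9.1% over both endpoints. A Cox model with timing plus shock rejects in 4.8-5.5% of runs in all settings, with median HR 0.99-1.00.

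**Step 3: sensitivity to the inputs.** A separate simulation used a 24-month median, a severity factor in 40-60% v 20%, severity HR 1.5-3, and 50+50, 50+150 or 100+100 patients. The unadjusted test rejected in about 6% to 68% of runs, with apparent HR about 1.08 to 1.59. A test stratified on the factor stayed near 5% (4.6% to 6.2%). With equal prevalence (30% in both groups) both tests stayed near 5%. The distortion comes from imbalance, and its size follows the inputs chosen.

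**The case against.** The strongest reply is that items 5 and 6 claim little. Items 2 and 4 set out to say whether treatment is an independent risk factor; items 5 and 6 announce only a comparison and call the method univariate. They also look secondary to the surgery question, although the SAP names no primary analysis. This bears on weight, but the plan never calls these items descriptive, and its 5% significance rule covers them.

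It is also fair that the magnitude carries no information from this document. Nothing in the SAP shows that the timing groups differ, and for item 6 the illustrated effect is slight at the mild end. The near-5% rate after adjustment is built in, because the one confounder simulated is the one adjusted for. All of this stands, and it is why the figures serve only as illustration.

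Adjustment is not a complete cure. Patients in a staged group must survive to their operation, and a covariate model does not remove that selection or unmeasured reasons for timing. This stands and should be stated with the results.

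Finally, a baseline table by timing group might be in the protocol, which is not at hand. It should therefore not count as a separate defect. The method line in items 5 and 6 is in the SAP itself and is not excused by that.

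**Conclusion.** The concern holds. Followed exactly, the plan yields four unadjusted tests of OS and RFS by timing in non-randomised groups, and no other item corrects them. That conclusion rests on the text alone.

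The size and direction of any bias are not derivable from the document. Under the assumptions above, item 5 could show an OS HR of about 1.08-1.21 (0.83-0.92 if the imbalance is reversed) with no timing effect at all, and a nominal 5% test would reject in about 6-14% of studies with 50 per group or 8-22% with 100. Item 6 is the weaker case: HR about 1.04-1.14, rejection about 5-9% with 30-50 per group. Several factors could differ at once, whereas the illustration uses one.

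The point affects the interpretation of items 5 and 6, not the surgery against no-surgery analyses. It should be fixed.

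**What to change.** For items 5 and 6, add a Cox model for OS and one for RFS with timing group plus a short, pre-specified set of covariates the plan already lists, such as hemorrhagic shock, Child-Pugh grade, tumor size, tumor number and MVI.

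- Use values recorded at presentation with the rupture. Values taken just before a staged operation may already be affected by the delay.
- Fix the order in which covariates enter and cap their number by the events available.
- Report the adjusted HR with its 95% CI, add a baseline table for each timing comparison, and keep the Kaplan-Meier/log-rank results as descriptive.
- State that survival to surgery and unmeasured reasons for timing remain as sources of bias.
- If events are too few for any adjustment, label both items descriptive and draw no conclusion about an effect of timing.

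The cost is SAP wording, four models (two comparisons × two endpoints) and two tables, provided the presentation values are on file.

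Intervals widen somewhat. In the OS illustration for item 5 with shock alone, the standard error of the log HR rises by about 3-9% against a fitted unadjusted model. Against the approximation 2/√d the rise is 4-10%; for example, 0.253 v 2/√76 = 0.229 in the stronger case with 50 per group. Further covariates would add to this.

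Small groups limit the model. With 30 per group the illustration gives about 45 OS events; at an assumed 10 events per parameter that allows four parameters, that is, timing plus three one-parameter covariates. The five examples above would not all fit, which is why the order of entry has to be fixed in advance.
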